### 8.3.2 Follow-up of AEs and SAEs

Any AEs that are unresolved at 90 days after last dose of IP should be followed up by the

investigator for as long as medically indicated, but without further recording in the eCRF. Redx retains the right to request additional information for any participant with ongoing AE(s)/SAE(s) at the end of the study, if judged necessary.

### **Adverse event variables**

'The following variables will be collected for each AE;

- AE (verbatim)
- The date when the AE started and stopped
- CTCAE grade changes
- Whether the AE is serious or not
- Investigator causality rating against the Investigational Product(s) (yes or no)
- Action taken with regard to Investigational Product(s)
- Outcome
- Whether treatment was required

In addition, the following variables will be collected for SAEs:

- Date AE met criteria for serious AE
- Date investigator became aware of serious AE
- Serious criteria
- Date of hospitalisation
- Date of discharge
- Probable cause of death
- Date of death
- Autopsy performed
- Causality assessment in relation to Study procedure(s)
- Causality assessment to other medication

#### **8.3.3 Causality Collection**

The investigator should assess causal relationship between Investigational Product and each Adverse Event, and answer 'yes' or 'no' to the question 'Do you consider that there is a reasonable possibility that the event may have been caused by the investigational product?'

#### **8.3.4 Adverse Events Based on Signs and Symptoms**

All AEs spontaneously reported by the patient or reported in response to the open question

from the study site staff: 'Have you had any health problems since the previous visit/you were last asked?', or revealed by observation will be collected and recorded in the eCRF. When collecting AEs, the recording of diagnoses is preferred (when possible) to recording a list of signs and symptoms. However, if a diagnosis is known and there are other signs or symptoms that are not generally part of the diagnosis, the diagnosis and each sign or symptom will be recorded separately.

### **8.3.5 Adverse Events Based on Examinations and Tests**

The results from the Clinical Study Protocol mandated laboratory tests and vital signs will be summarised in the Clinical Study Report (CSR).

Deterioration as compared to baseline in protocol-mandated, laboratory values, vital signs, bone turnover biomarkers and DXA scans, should therefore only be reported as AEs if they fulfil any of the SAE criteria, are the reason for discontinuation of treatment with the investigational product or are considered to be clinically relevant as judged by the investigator (which may include but not limited to consideration as to whether treatment or non-planned visits were required or other action was taken with the study treatment, e.g. dose adjustment or drug interruption).

If deterioration in a laboratory value/vital sign is associated with clinical signs and symptoms, the sign or symptom will be reported as an AE and the associated laboratory result/vital sign will be considered as additional information. Wherever possible the reporting investigator uses the clinical, rather than the laboratory term (e.g. anaemia versus low haemoglobin value). In the absence of clinical signs or symptoms, clinically relevant deteriorations in non-mandated parameters should be reported as AE(s).

Deterioration of a laboratory value, which is unequivocally due to disease progression, should not be reported as an AE/SAE.

Any new or aggravated clinically relevant abnormal medical finding at a physical examination as compared with the baseline assessment will be reported as an AE unless unequivocally related to the disease under study.

### **8.3.6 Hy's Law**

If a patient demonstrates an AST or ALT  $\geq 3$  x ULN together with total bilirubin  $\geq 2$  x ULN, it must be reported to the Sponsor and/or designated CRO within 24 hours. Prompt reporting of cases meeting Hy's Law criteria (via the SAE expedited reporting system) is required for compliance with regulatory guidelines. The Investigator is responsible for immediately determining whether a patient meets potential Hy's Law criteria. The Investigator needs to perform additional examinations for this and confirm the results with the medical monitor.

### 8.3.7 Disease Progression

Disease progression can be considered as a worsening of a patient's condition attributable to the disease for which the investigational product is being studied. It may be an increase in the severity of the disease under study and/or increases in the symptoms of the disease. The development of new, or progression of existing metastasis from the primary cancer under study should be considered as disease progression and not an AE. Events, which are unequivocally due to disease progression, should not be reported as an AE during the study.

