### 8.3.8 Disease Under study

Events which are unequivocally due to disease under study should not be reported as an AE during the study unless they meet SAE criteria or lead to discontinuation of the investigational product.

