### 8.3.9 Reporting of Serious Adverse Events

All SAEs must be reported, whether or not considered causally related to the investigational product, or to the study procedure(s). All SAEs will be recorded in the eCRF.

If any SAE occurs in the course of the study, then investigators or other site personnel must inform the appropriate Sponsor representatives within one day i.e., immediately but **no later than 24 hours** of when he or she becomes aware of it.

The designated Sponsor representative works with the investigator to ensure that all the necessary information is provided to Patient Safety **within 1 calendar day** of initial receipt for fatal and life-threatening events **and within 5 calendar days** of initial receipt for all other SAEs.

For fatal or life-threatening adverse events where important or relevant information is missing, active follow-up is undertaken immediately. Investigators or other site personnel inform Sponsor representatives of any follow-up information on a previously reported SAE within one calendar day i.e., immediately but **no later than 24 hours** of when he or she becomes aware of it.

For further guidance on the definition of a SAE, see Appendix B of the Clinical Study Protocol.

The reference document for definition of expectedness is the IB for RXC004 and the EU/FDA/Local label for nivolumab.

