### **B 2 Definitions of serious adverse event**

A serious adverse event is an AE occurring during any study phase (i.e., run-in, treatment, washout, follow-up), that fulfils one or more of the following criteria:

- Results in death
- Is immediately life-threatening
- Requires in-participant hospitalisation or prolongation of existing hospitalisation
- Results in persistent or significant disability or incapacity
- Is a congenital abnormality or birth defect
- Is an important medical event that may jeopardise the participant or may require medical treatment to prevent one of the outcomes listed above.

Adverse Events (AEs) for **malignant tumours** reported during a study should generally be assessed as **Serious** AEs. If no other seriousness criteria apply, the 'Important Medical Event' criterion should be used. In certain situations, however, medical judgement on an individual event basis should be applied to clarify that the malignant tumour event should be assessed and reported as a **Non-Serious** AE. For example, if the tumour is included as medical history and progression occurs during the study, but the progression does not change treatment and/or prognosis of the malignant tumour, the AE may not fulfil the attributes for being assessed as Serious, although reporting of the progression of the malignant tumour as an AE is valid and should occur. Also, some types of malignant tumours, which do not spread remotely after a routine treatment that does not require hospitalization, may be assessed as Non-Serious; examples in adults include Stage 1 basal cell carcinoma and Stage 1A1 cervical cancer removed via cone biopsy.

The above instruction applies only when the malignant tumour event in question is a new malignant tumour (i.e., it is *not* the tumour for which entry into the study is a criterion and that is being treated by the IP under study and is not the development of new or progression of existing metastasis to the tumour under study). Malignant tumours that – as part of normal, if rare, progression – undergo transformation (e.g., Richter's transformation of B cell chronic lymphocytic leukaemia into diffuse large B cell lymphoma) should not be considered a new malignant tumour.

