Explain if first use TEAEs with missing relationship to the study drug will be considered as related. AEs will be coded using the MedDRA, latest version. Grading will be performed using CTCAE version 5.0.

TEAEs are defined as those AEs with an onset after dosing and those pre-existing AEs that worsen after the start of dosing and within 30 days of stopping RXC004 monotherapy or 90 days after the last actual Nivolumab dose (for patients on RXC004 and Nivolumab combination).

An overview table of TEAEs will be provided showing the number of patients, the percentage of patients and the number of events for the following categories of events:

- Any TEAE
- Any treatment related TEAE to RXC004
- Any treatment related TEAE to Nivolumab
- Any grade ≥ 3 TEAE
- Any grade ≥ 3 TEAE related to RXC004
- Any grade ≥ 3 TEAE related to Nivolumab
- Any serious TEAE (STEAE)
- Any serious TEAE related to RXC004
- Any serious TEAE related to Nivolumab
- Any TEAE leading to death
- Any TEAE leading to permanent discontinuation or reduction or interruption of RXC004
- Any TEAE leading to permanent discontinuation of RXC004
- Any TEAEs leading to RXC004 reduction
- Any TEAEs leading to RXC004 interruption
- Any TEAE leading to permanent discontinuation or interruption of Nivolumab
- Any TEAE leading to permanent discontinuation of Nivolumab
- Any TEAEs leading to Nivolumab interruption

For TEAEs, TEAEs considered related (RXC004 and Nivolumab), STEAEs, STEAEs considered related (RXC004 and Nivolumab), TEAEs leading to study treatment discontinuation, TEAEs leading to RXC004 reduction, TEAEs leading to RXC004 interruption, TEAEs leading to Nivolumab interruption, TEAEs by maximum grade, TEAEs with grade ≥ 3 , TEAEs with grade ≥ 3 related to RXC004, TEAEs with grade ≥ 3 related to Nivolumab, death, detailed tables will be created showing the number of patients who experienced at least one TEAE, the corresponding percentage of patients and the number of events by SOC and PT.

SOC will be sorted by alphabetical order. PTs, within each SOC, will be sorted by descending order of total frequency. In the event of PTs with equal total frequencies, the relevant PTs will be sorted

alphabetically.. In addition, a table summarizing TEAEs by decreasing frequency of Preferred Terms will be produced for all TEAEs and TEAEs related to RXC004/Nivolumab.

A table will also be produced showing the details for every patient that die (death date, cause of death etc...).

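### Protocol 8.3.7 and 8.3.8 give opposite reporting rules for serious, fatal or treatment-ending events caused by worsening cancer, and no text says which prevails

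*Protocol*

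**What the plan says.** **Protocol 8.3.7 (Disease Progression)** excludes progression events from AE reporting and lists no exception: "Events, which are unequivocally due to disease progression, should not be reported as an AE during the study". It also says what progression can consist of: "It may be an increase in the severity of the disease under study and/or increases in the symptoms of the disease".

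**Protocol 8.3.8 (Disease Under study)** states that events unequivocally due to that disease "should not be reported as an AE during the study unless they meet SAE criteria or lead to discontinuation of the investigational product".

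**Protocol 8.3.9 (Reporting of Serious Adverse Events)** adds a general duty: "All SAEs must be reported, whether or not considered causally related to the investigational product". It mentions neither progression nor discontinuation. Appendix B 2 builds the SAE on the AE: "A serious adverse event is an AE occurring during any study phase". Death and hospitalisation are among its seriousness criteria.

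**SAP 6.1.4** carries the 8.3.7 exclusion in the same words and omits the 8.3.8 exception.

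**SAP 4.12.1** counts serious TEAEs, TEAEs leading to discontinuation and "Any TEAE leading to death" from whatever was recorded. It has no rule for separating or removing progression events. The same section plans a table with date and cause of death for every patient who dies.

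**The concern.** Two adjacent paragraphs appear to govern the same events and reach different answers. Take a patient admitted with bowel obstruction from a growing tumour. A site working from 8.3.7 records nothing. A site working from 8.3.8 records an SAE, which 8.3.9 requires within 24 hours.

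Safety and tolerability is a secondary objective in each arm, with incidence of AEs, SAEs and discontinuations among its endpoints. If the practice varies between sites, part of what the SAP tables show is reporting habit. A reader of those tables could not tell, because nothing in the SAP identifies which serious or fatal TEAEs were due to progression.

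**Working it through.** The plan states no figure on this point, so the check is mainly a comparison of text.

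**Step 1. Do the two rules cover the same events?** The headings differ, and 8.3.8 speaks of the disease under study where 8.3.7 speaks of progression. But 8.3.7 defines progression through the severity and symptoms of the disease under study. Anything caused by progression in that sense is also caused by the disease under study. Both rules are limited to unequivocal cases, so that qualifier does not separate them.

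**Step 2. What does each rule give for an event that is unequivocally due to worsening cancer?**

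| Event | 8.3.7 | 8.3.8 |
|---|---|---|
| Not serious, treatment continues | not reported | not reported |
| Meets SAE criteria, including death | not reported | reported |
| Leads to discontinuation | not reported | reported |

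The rules agree on the first row and conflict on the other two.

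**Step 3. Does other text settle it?**

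- 8.3.9 covers SAEs whatever their causality. Because Appendix B 2 makes an SAE a kind of AE, a site following 8.3.7 can say there is no AE for 8.3.9 to act on. It also says nothing about non-serious events that end treatment.
- 8.3.5 has a parallel rule for laboratory values: "Deterioration of a laboratory value, which is unequivocally due to disease progression, should not be reported as an AE/SAE". It excludes both categories by name, whereas 8.3.7 names only the AE. This can be read as showing that the authors wrote an SAE exclusion where they wanted one, or as showing a general intent to leave progression out.
- Appendix B 3 tells investigators how to rate causality when the disease has deteriorated through lack of effect. That presupposes that some such cases are recorded.
- SAP 6.1.4 repeats one side only.

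None of these states precedence.

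**Step 4. Which outputs are exposed?**

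- Exposed: the SAP 4.12.1 counts of serious TEAEs, TEAEs leading to death and TEAEs leading to discontinuation.
- Not exposed: total deaths, the by-patient deaths table and overall survival. Survival status is followed separately (Protocol 8.1.2, SAP 3.2.1.6).

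**Step 5. Scale.** Protocol 4.1 plans 20 evaluable patients per arm. The safety tables use the full analysis set, whose planned size is redacted, so 20 serves only as a scale. If k patients have a progression event as their only event in a category, the incidence shifts by k/20:

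- k = 1: 1/20 = 5 percentage points
- k = 2: 2/20 = 10 percentage points
- k = 5: 5/20 = 25 percentage points

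The values of k are assumptions, since the documents give no expected number. Evaluable patients must have been dosed, so an arm that reaches 20 of them has a full analysis set of at least 20. In that case 5 points is the most that one patient can move an incidence.

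**The case against.** The best defence is that the paragraphs divide the field: 8.3.7 is the specific rule for progression, and 8.3.8 is the general rule for other consequences of the disease. There is support for this. The laboratory rule in 8.3.5 excludes progression even as an SAE. Appendix B 2 takes new or progressing metastasis of the study tumour out of its instruction on malignant tumours. SAP 6.1.4 carries only the progression rule. The reading makes divergence between sites less certain, so the right word is could. It does not remove the overlap that the 8.3.7 definition creates, and Appendix B 3 points the other way. It also has an odd consequence: a serious event from unchanged disease would be reportable while one from worsening disease would not.

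It is also fair to say that making serious progression events reportable is a preference. Extending the 8.3.7 exclusion to 8.3.8 would be equally consistent. That stands, and the direction is the sponsor's choice.

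A reader might infer more than the documents support:

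- **That 8.3.9 itself requires progression events that are serious or end treatment.** It names neither progression nor discontinuation. The explicit exception is in 8.3.8 alone.
- **That the conflict creates a false SAE excess in Arm B**, because collection runs 90 days after the last nivolumab dose against 30 days after the last RXC004 dose on monotherapy. Arm A patients who cross over also get the 90-day window, so the windows do not divide cleanly by arm. The difference in length exists under either paragraph, and no formal comparison of the arms is planned.
- **That the number of deaths at issue can be estimated** from the median survival of about 6 months in Protocol 2.3.3. That figure belongs to third-line comparator agents and would give deaths from any cause, which does not measure this inconsistency.

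**Conclusion.** The inconsistency is real and lies in current protocol text. For an event that is unequivocally due to worsening cancer and is serious, fatal or treatment-ending, 8.3.7 and 8.3.8 give opposite instructions with no stated precedence. The consequence is possible site-to-site variation in three groups of SAP 4.12.1 counts. Its total size cannot be estimated from the documents; only the step per affected patient can.

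The conclusion rests on reading the 8.3.7 description of progression as written, and on sites not having been given a resolving instruction elsewhere. Completion guidelines and the safety committee charter are not among the documents. It does not reach the efficacy endpoints or mortality. It is worth correcting because the correction is small and the affected counts serve a secondary objective.

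**What to change.** 1. **Protocol.** Reconcile 8.3.7 and 8.3.8 into one rule for serious, fatal and treatment-ending events due to progression. The smallest edit is to give 8.3.7 the exception already in 8.3.8, worded so that radiological progression alone is not recorded as an AE leading to discontinuation. Protocol 7.1 makes RECIST progression a reason to stop treatment, so a loosely worded exception could pull in every such patient.
2. **SAP 6.1.4.** Align the repeated AE sentence with the reconciled rule, or delete it, since it has no role in deriving overall response.
3. **SAP 4.12.1.** Show serious TEAEs, TEAEs leading to death and TEAEs leading to discontinuation in total and again excluding those due to progression. An eCRF flag would be the cleanest source. Without one, identify the events from recorded terms and cause of death, and state that rule before the tables are run.

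**Cost.** One protocol clause, one SAP sentence, a few table rows and some additional SAE reports. An eCRF flag added this late (SAP version 4.0 is dated May 2024) would mean re-querying events already collected. The SAP tabulation can be done without it, but it cannot recover events that a site never recorded, and the report should say so.

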### 8.3.8 Disease Under study

Events which are unequivocally due to disease under study should not be reported as an AE during the study unless they meet SAE criteria or lead to discontinuation of the investigational product.

### 8.3.9 Reporting of Serious Adverse Events

All SAEs must be reported, whether or not considered causally related to the investigational product, or to the study procedure(s). All SAEs will be recorded in the eCRF.

If any SAE occurs in the course of the study, then investigators or other site personnel must inform the appropriate Sponsor representatives within one day i.e., immediately but **no later than 24 hours** of when he or she becomes aware of it.

The designated Sponsor representative works with the investigator to ensure that all the necessary information is provided to Patient Safety **within 1 calendar day** of initial receipt for fatal and life-threatening events **and within 5 calendar days** of initial receipt for all other SAEs.

For fatal or life-threatening adverse events where important or relevant information is missing, active follow-up is undertaken immediately. Investigators or other site personnel inform Sponsor representatives of any follow-up information on a previously reported SAE within one calendar day i.e., immediately but **no later than 24 hours** of when he or she becomes aware of it.

For further guidance on the definition of a SAE, see Appendix B of the Clinical Study Protocol.

The reference document for definition of expectedness is the IB for RXC004 and the EU/FDA/Local label for nivolumab.

### 8.3.10 Pregnancy

All pregnancies and outcomes of pregnancy should be reported to Sponsor representative except for if the pregnancy is discovered before the study participant has received any study

drug.

### **8.3.10.1 Maternal Exposure**

The Sponsor and Sponsor designated Safety Services must be notified **within 24 hours** of the initial report and any follow-up reports of a female patient or a male patient's female partner becoming pregnant during the course of the study and for 5 months after the last dose of the study drug(s) via the Pregnancy Report Form. Pregnancy itself is not regarded as an adverse event unless there is a suspicion that the investigational product under study may have interfered with the effectiveness of a contraceptive medication or a female patient or male patient's female partner experiences signs or symptoms of pregnancy complications; congenital abnormalities/birth defects and spontaneous miscarriages should be reported as SAEs. The contact information for pregnancy reporting is the same as for SAE reporting. Female patient(s) who become pregnant will be followed until the outcome of the pregnancy is known. In order for the Sponsor or designee to collect pregnancy surveillance information, the pregnant patient or partner must sign an ICF. Pregnancy follow-up should describe the outcome of the pregnancy, including any voluntary or spontaneous termination, details of the birth, and the presence or absence of any congenital abnormalities or birth defects in the offspring.

If a female patient becomes pregnant, administration of the study drug(s) must be discontinued immediately.

### **8.3.10.2 Paternal Exposure**

Male participants should refrain from fathering a child or donating sperm during the study and for at least 5 months following the last dose.

Pregnancy of the participant's partners is not considered to be an adverse event. However, the outcome of all pregnancies (spontaneous miscarriage, elective termination, ectopic pregnancy, normal birth or congenital abnormality), occurring from the date of the first dose until 5 months after the last dose should, if possible, be followed up and documented in the Pregnancy Report Form. Consent from the partner must be obtained before the Pregnancy Report Form is completed.

